2.1.1. Study population

The study population will consist of adults with NVAF who are newly prescribed apixaban or warfarin with at least one high bleeding risk. Further information on patient selection and enrolment and follow-up time periods are available in Subsection 9.2 of the protocol.

2.1.2. Data source

The analysis will be based on administrative data from MDV Co. Ltd., a longitudinal database based on health insurance claims and medical records obtained from the hospitals in which the DPC payment system for utilization of both inpatient and outpatient hospital claims (percentage of inpatients is about 20%). The database provides claims data from 449 hospitals (as of Aug 2021) using the DPC system for medical service claims (26% of general hospitals in Japan is under the DPC system) including approximately 36.7 million patient data.

2.1.3. Treatment/cohort labels

For primary analysis,

- IPTW-balanced apixaban cohort: NVAF patients de novo diagnosis with NVAF and initiate apixaban and have at least one risk factor(s) of bleeding.
- IPTW-balanced warfarin cohort: NVAF patients de novo diagnosis with NVAF and initiate warfarin and have at least one risk factor(s) of bleeding.

Patients will be assigned to each cohort based on the first prescription of oral anticoagulants after the diagnosis of NVAF (warfarin or apixaban). If the 1st prescribed oral anticoagulants are not warfarin

nor apixaban, the patients will be excluded. Patient clinical and demographic characteristics will be balanced by using IPTW methods.

2.2. STUDY OBJECTIVES

2.2.1. The research questions:

- 1. Are there any differences in the risk of major bleeding between apixaban and warfarin for patients with higher bleeding risk(s) in the general practice settings in Japan?
- 2. Are there any differences in the risk of stroke/systemic embolism(SE) between apixaban and warfarin for patients with higher bleeding risk(s) in the general practice settings in Japan?

2.2.2. The primary objective of the study

To compare effectiveness (a composite risk of stroke/SE) and safety (major bleeding events) of warfarin and apixaban among NVAF patients with at least one bleeding risk (that is, patients at higher risk of bleeding)

2.2.3. The secondary objectives are

- 1. To compare the risk of major gastrointestinal or intracranial bleeding between warfarininitiators and apixaban-initiators in patients with at least one bleeding risk.
- 2. To compare the risk of ischemic stroke, hemorrhagic stroke or SE between warfarin-initiators and apixaban-initiators in patients with at least one bleeding risk.

F

2.2.4. Objectives of other exploratory analysis are

To explore the risk of major bleeding and stroke/SE in the specific populations at higher bleeding risk(s).

As shown above (see 2.1), after interaction analyses of the treatment and risk factors, patients will be stratified to subgroups by each of above mentioned 15 predetermined risk factors separately. Subgroups with adequate sample size will be selected for IPTW analyses.

In the previous feasibility analysis, we found that the numbers of patients with hemorrhagic stroke, alcohol abuse, chronic concomitant used of NSAIDs (for continuously > 90 days), and refractory hypertension were less than 2,000. Due to the insufficient statistical power, these subgroups could be eliminated from the further subgroup analysis. Again, the final decision will be based on the formal evaluation of the number of sample sizes N in those subgroups.

Candidates of exploratory subgroups listed based on the preliminary feasibility analysis

- Exploratory analysis regarding hypertension
- *Exploratory analysis regarding liver dysfunction.*
- Exploratory analysis regarding renal impairment.
- *Exploratory analysis regarding bleeding including intracranial hemorrhage*
- Exploratory analysis regarding concomitant use of antiplatelet drug
- *Exploratory analysis by age*
 - \checkmark > 80 y
 - \checkmark >90 y
- Exploratory analysis regarding peptic ulcer
- Exploratory analysis regarding active cancer
- *Exploratory analysis regarding low body weight (<40kg)*
- Exploratory analysis regarding diabetes mellitus
- *Exploratory analysis regarding polypharmacy (≥6 medicines)*

3. HYPOTHESES AND DECISION RULES

3.1. STATISTICAL HYPOTHESES

This study includes specific hypotheses to be tested. The null hypothesis for each objective is as follows:

Null: The risks of each of the following endpoints do not differ between NVAF patients treated with warfarin and patients treated with apixaban even if the patients have at least one bleeding risk.

- Major Bleeding
- A composite of stroke/SE

3.2. STATISTICAL DECISION RULES

For primary safety and effectiveness analyses, all statistical tests will be performed at p=0.05 (twosided) with no adjustment for multiplicity. Since we will conduct various multiple subgroup analyses, which lead to the "Multiple Testing Problem". Here these subgroup analyses will be conducted with an exploratory purpose and we do not plan to conclude anything from the results here. Therefore, we will not adjust the p values and still the use p<0.05 to indicate the statistical significance.

4. ANALYSIS SETS/POPULATIONS

4.1. FULL ANALYSIS SET

This study uses data from the MDV database, which includes the data used for both inpatient and outpatient insurance claims by hospitals according to the Diagnosis Procedure Combination (DPC) procedure.

The study population will consist of adults with NVAF who are newly prescribed apixaban or warfarin. Follow-up time period starts from the next day of the index date, and ends depending on following outcomes which observed first.

4.1.1. Inclusion criteria

Patients must meet all of the following inclusion criteria to be eligible for inclusion in the study:

- 1. Patients with diagnosis with NVAF anytime in the baseline period or on the index date,
- 2. The first prescribed anticoagulant is apixaban or warfarin after the index date.
- 3. No use of the any oral anticoagulants (OACs) during the baseline period (the 180 days before the index date)
- 4. Age of 18 years or older on the index date.

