9.2.1. Inclusion criteria

Patients must meet all of the following inclusion criteria to be eligible for inclusion in the study:

- 1. Diagnosed with AF anytime in the baseline period or on the index date, also have definitive diagnosis of AF anytime in the baseline period, on the index date, or post-index period.
- 2. Prescribed apixaban or wararin on or after the day of AF diagnosis. The first observed prescription will be used to identify the patient's index date and treatment cohort
- 3. No use of the any OACs during the baseline period (the 180 days before the index date)
- 4. Age of 18 years or older on the index date.

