First, all patients with NVAF who are newly diagnosed and initiated apixaban or warfarin will be extracted from the database. Among these patients, patients with at least one predetermined high bleeding risks will be extracted. In this study, predetermined high bleeding risks are 1) patients with hypertension diagnosis, 2) patients with liver dysfunction, 3) patients with renal dysfunction diagnosis, 4) patients with a history of bleeding, 5) patients with hemorrhagic stroke, 6) patients with alcohol abuse, 7) patients with concomitant used of antiplatelet drugs, 8) patients with chronic (continuously for longer than 90 days) concomitant use of Non-steroidal antiinflammatory drug (NSAID), 9) highly elderly (> 80 years old), 10) patients with refractory hypertension, 11) patients with a history of peptic ulcer diagnosis, 12) patients with active cancer, 13) patients with diabetes mellitus, 14) patients whose body weight is <40kg, 15) patients with polypharmacy (sea Section 5.4 for the definition). Patients with at least one predetermined high bleeding risk factor will be divided into two cohorts, apixaban and warfarin cohorts, based on the first prescribed drug just after the NVAF diagnosis. Patient characteristics will be balanced by using an inverse probability of treatment weighting (IPTW) method to create balanced apixaban and balanced warfarin cohorts. Comparisons will be conducted by using these balanced warfarin and apixaban cohorts (Kaplan-meier curves, incidence rates per 1,000 person-year and hazard ratio with 95% confident intervals). The primary safety and effectiveness analyses are comparison of apixaban with warfarin in patients with at least one predetermined risk factor for bleeding.

- Second, after the first analysis, we will conduct separate interaction analysis of the treatment (apixaban vs. warfarin) and one of the 15 risk factors (e.g., hypertension yes vs no, etc) to see if treatment effects are consistent among patients with or without each specific factor
- Third, patients will be stratified by risk factors into 15 subgroups, and same IPTW analyses as described in the step 1 will be conducted only in the subgroups with adequate sample sizes.

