4.1.3.2. Index date

The date when patients initiated warfarin or apixaban

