7. STATISTICAL METHODOLOGY AND STATISTICAL ANALYSES

7.1. STATISTICAL METHODS

7.1.1. Calculation of Propensity Score

In this study, balanced cohorts (apixaban vs. warfarin) will be created by an IPTW method. Propensity scores will be estimated by unconditional logistic regression analyses that incorporate potential predictors of therapy as independent variables in the regression and cohort status as the outcome. Using calculated propensity score an IPTW method will be applied to balance the warfarin and apixaban cohorts, which will be used for the comparisons of all endpoints (sections 5.1 and 5.2). The following covariates will be included in the logistic regression for calculation of propensity score:

• age on index date

- gender
- CHADS2 score in baseline
- CHA2DS2-VASc score in baseline
- heart failure diagnosis in baseline
- coronary heart disease diagnosis in baseline
- peripheral arterial disorder diagnosis in baseline
- myocardial infarction diagnosis in baseline
- hyperthyroidism or thyrotoxicosis in baseline
- TIA diagnosis in baseline
- stroke or SE diagnosis in baseline
- renal dysfunction diagnosis in baseline
- liver dysfunction diagnosis in baseline
- bleeding diagnosis in baseline
- hypertension diagnosis in baseline
- diabetes mellitus diagnosis in baseline
- treated with antiplatelet drug in baseline
- treated with NSAIDs in baseline
- treated with gastric secretion inhibitor in baseline
- treated with statin-based drug in baseline
- treated with anti-hypertensives in baseline
- treated with anti-arrhythmics in baseline
- treated with beta-blockers in baseline
- treated with heparins in baseline
- cardioversion in baseline

The operational definitions for the above covariates are shown in the Section 5.4.

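### SAP inclusion criterion 2 tests the first anticoagulant after the index date, which contradicts the SAP's own index-date definition and the cohort rules elsewhere; programmed literally, it decides eligibility on a prescription inside follow-up

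*SAP*

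**What the plan says.** Five places bear on who enters the study and when.

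- SAP 4.1.1, criterion 2: "The first prescribed anticoagulant is apixaban or warfarin after the index date". Patients must meet every criterion in that list.
- SAP 4.1.3.2 defines the index date: "The date when patients initiated warfarin or apixaban".
- SAP 2.1.3: "Patients will be assigned to each cohort based on the first prescription of oral anticoagulants after the diagnosis of NVAF". Patients whose first such drug is neither warfarin nor apixaban are excluded.
- SAP 2.1 divides the cohorts "based on the first prescribed drug just after the NVAF diagnosis".
- Protocol 9.2.1, criterion 2: "Prescribed apixaban or wararin on or after the day of AF diagnosis", followed by "The first observed prescription will be used to identify the patient's index date and treatment cohort".

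Three further provisions matter. Under SAP 4.1.3.1, follow-up begins the day after the index date, and patients who discontinue, withdraw or switch are censored. Criterion 3 in SAP 4.1.1 speaks of oral anticoagulants, whereas criterion 2 says only anticoagulant. The propensity model in SAP 7.1.1 includes "treated with heparins in baseline", so patients exposed to heparin are expected in the cohort.

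**The concern.** The prescription that starts treatment is on the index date by definition. A test applied after that date must look at some later prescription, and follow-up is already running by then. Eligibility would then depend on what happened to the patient after time zero.

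Patients never prescribed apixaban or warfarin again would be lost. Some of them may have stopped because of a bleed or a stroke, and these are the two primary endpoints. The planned methods would not repair this. Weighting in SAP 7.1.2 balances only the patients who were included, and the E-values in SAP 7.1.8 address unmeasured confounding, not selection on information after the index date.

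SAP 4.1.1 is the list a programmer will implement. Protocol 9.7 allows the SAP to modify the protocol's plans, so the programmer cannot simply assume that the protocol wording prevails.

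**Working it through.** **Reading the clause.** In a patient with no oral anticoagulant during the 180-day baseline, the first apixaban or warfarin prescription is the index prescription. If first means first overall, nobody can satisfy a test placed after the index date. The clause can be programmed only if first means first among the records after index. The table takes that reading and compares it with the rule in SAP 2.1.3 and Protocol 9.2.1, with censoring by SAP 4.1.3.1.

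| Pattern after a qualifying index prescription | Criterion 2, literal | SAP 2.1.3 / Protocol 9.2.1 with SAP 4.1.3.1 |
|---|---|---|
| No further anticoagulant, later encounters on record | Excluded | Included; censored as discontinued at the supposed refill date |
| No further anticoagulant, no data after the refill date | Excluded | Included; censored as withdrawn at the last encounter |
| Next anticoagulant is an oral drug other than apixaban or warfarin | Excluded | Included; censored at the switch |
| Warfarin followed by apixaban, or the reverse | Included | Included; censored at the switch |
| Heparin is the first anticoagulant record after index | Excluded, because oral is missing | Included; heparin is not a switch |
| Heparin only before or on the index date | No effect | Included |
| Bleed or stroke, then apixaban or warfarin prescribed as the next anticoagulant | Included; the event counts | Included; the event counts |

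The two rules disagree in four rows. In the first three of these, SAP 4.1.3.1 already gives the patient a defined end of follow-up, so one section of the SAP would exclude patients whom another part of it censors.

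**Same-day starts.** Criterion 1 of SAP 4.1.1 accepts a diagnosis on the index date, and Protocol 9.2.1 accepts a prescription on the day of diagnosis. SAP 2.1 and 2.1.3 say after the diagnosis, which read strictly drops patients diagnosed and started on the same day.

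**Is sample size at stake?** The plan's own figures in SAP 7.1.9 come first.

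- Events = (1.960 + 0.842)² / (0.25 × (ln 0.7)²) = 246.8; the SAP states 246.
- Major bleeding: mean rate (3.77% + 2.50%)/2 = 3.135% a year; 246/0.03135 = 7,847; the SAP states 7,846.
- Stroke/SE: mean rate (2.77% + 1.79%)/2 = 2.28% a year; 246/0.0228 = 10,789, as stated.

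These figures imply one person-year per patient. SAP 7.1.9 reports more than 10,000 eligible patients in each cohort. Taking exactly 10,000 per arm, one person-year each, a hazard ratio of 0.7 and no allowance for weighting:

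- Stroke/SE events = 20,000 × 0.0228 = 456, and power = Φ(√(456 × 0.25) × 0.3567 − 1.960) = 96.8%.
- Major bleeding power on the same basis is 99.4%.
- If both arms lost patients equally, stroke/SE power would fall to about 80% only at a 46% loss (about 10,788 patients left).
- If only the warfarin arm lost patients, stroke/SE power would be 95.8% at a 10% loss, 92.4% at 30% and 85.0% at 50%.

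These losses are a range of assumptions, since the documents give none. Moderate loss would not undermine the stated power. What remains is selection on information after the index date.

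**The case against.** The strongest reply is that this is a slip in one clause. Taken strictly the clause contradicts itself, no passage states a second-prescription rule, and SAP 2.1, SAP 2.1.3 and Protocol 9.2.1 all count from diagnosis. SAP 2.1.1 also sends the reader to Protocol 9.2 for patient selection. The censoring rules in SAP 4.1.3.1 assume that patients without a refill, and patients who switch, are in the analysis. All of this stands, and it shows what was probably intended. It does not remove the need to correct the operative list, because the SAP points to one rule and states another.

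Three stronger readings are tempting, and the documents support none of them.

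- **Guaranteed event-free time.** A reader might infer that everyone included must survive event-free to the next prescription. The clause requires only a later prescription of apixaban or warfarin. A patient who bleeds and is then prescribed again still qualifies, and the event counts.
- **Loss of heparin-treated warfarin starters as a group.** Only heparin recorded after index, and before any later apixaban or warfarin record, triggers exclusion.
- **More damage to the warfarin arm.** The documents give no heparin use by arm and no count of heparin records after index, so a difference between arms is conjecture.

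**Conclusion.** The contradiction is real and lies in an operative eligibility criterion. SAP 4.1.1 criterion 2 cannot be reconciled with SAP 4.1.3.2, and it differs from SAP 2.1, SAP 2.1.3 and Protocol 9.2.1 in both its time anchor and its drug class. Taken literally, it excludes patients with no anticoagulant prescription after the index one and patients whose next anticoagulant is neither apixaban nor warfarin.

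It is most likely a drafting error; under the rule stated in the other passages, none of these patients is dropped. The harm therefore depends on the clause being programmed as it stands. The documents report neither how many patients have a single prescription nor how many have heparin or another oral anticoagulant next. The size and direction of any bias, and any difference between the arms, cannot be stated. The point does not rest on power, and it does not show that the study has adopted a two-prescription design.

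**What to change.** Replace criterion 2 in SAP 4.1.1 with a rule to this effect: the first oral anticoagulant prescribed on or after the AF diagnosis date is apixaban or warfarin; the date of that prescription is the index date, and that drug defines the cohort. Add that no prescription after the index date is needed for eligibility, and that heparin, whenever given, does not count for this criterion. Use the same on-or-after timing in SAP 2.1 and 2.1.3, so that patients diagnosed and started on the same day, whom criterion 1 allows, are kept.

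The cost is a few sentences in the SAP, before the selection program is written. It needs no further data and no change to Protocol 9.2.1.

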4.1.3. Definitions

4.1.3.1. Follow-up period

Follow-up time period starts from the next day of the index date, and ends depending on following outcomes which observed first.

- 1. Major bleeding when the target outcome for the analysis is major bleeding.
- 2. Composite of (ischemic or hemorrhagic) stroke and SE when the target outcome for the analysis is the composite endpoint.
- 3. Discontinuation of apixaban or warfarin: The index treatment will be considered to be "discontinued" if apixaban or warfarin is not prescribed within 45 days after prescription refill date (calculated from the last refill date plus days of supply) of apixaban or warfarin, even though the patient has >1 medical encounter records after more than 45 days following the prescription refill date. The supposed prescription refill date is regarded as the last day of the follow-up for discontinued patients.
- 4. Switching from apixaban or warfarin: The index treatment is regarded as "switched" if the OAC is prescribed within 45 days after prescription refill date of apixaban or warfarin when the patient has 1> medical encounter records after more than 45 days following the prescription refill date. The switched day is regarded as the last day of the follow-up for the switched patients.
- 5. Withdrawal from the database: The patients are regarded as "withdrawal" from the database if apixaban or warfarin is not prescribed within 45 days after prescription refill date of the apixaban or warfarin and there is no data of the patient on the database after prescription refill date. The last medical encounter is regard as the last day of the follow-up for patients withdrawn from the database.
- 6. An elapse of 2 years from the index date without any of the event above.

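### No observed history is required before the index date, so OAC-naive status can rest on absent records; the primary cohort is affected in two identifiable groups

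*SAP*

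**What the plan says.** The new-user criterion in SAP 4.1.1 is "No use of the any oral anticoagulants (OACs) during the baseline period (the 180 days before the index date"; Protocol 9.2.1 has the same 180-day window. The AF criterion is wider: "Patients with diagnosis with NVAF anytime in the baseline period or on the index date" (SAP 4.1.1), and likewise "Diagnosed with AF anytime in the baseline period or on the index date" (Protocol 9.2.1). The index date is named there as an addition, so the baseline period stops before it. SAP 4.1.3.2 defines the index date as "The date when patients initiated warfarin or apixaban", and SAP 4.1.3.1 adds "Follow-up time period starts from the next day of the index date".

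SAP 5.4 sets each diagnosis or drug covariate to 1 if a code appears during the baseline period. Age, sex, physician specialty, hospital size and hospitalization status are read at the index date.

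The source is "a longitudinal database based on health insurance claims and medical records obtained from the hospitals" (SAP 2.1.2). The apixaban cohort is described as "NVAF patients de novo diagnosis with NVAF and initiate apixaban" (SAP 2.1.3, with a parallel label for warfarin), and the Protocol abstract calls the population treatment-naive. Neither document asks for an earlier encounter, a minimum time in the database, or an index date at least 180 days after the data begin.

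**The concern.** Care given outside a contributing hospital leaves no trace in that hospital's claims. A patient already anticoagulated elsewhere can then appear as a new user at the first recorded prescription. The comparison is presented as one of initiators. If some patients are in fact prevalent users, and their share or their hazard differs between arms, the hazard ratio no longer compares initiators with initiators.

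The same lack of records also affects confounding control. Unrecorded comorbidity enters the propensity score as absent rather than missing, and weighting cannot balance what was not captured. Diagnoses coded on the index date itself count in neither the baseline period nor follow-up.

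**Working it through.** **1. Windows.** Baseline is the 180 days before the index date, and follow-up starts the day after it. A comorbidity coded only on the index date is therefore used nowhere, apart from the AF diagnosis.

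**2. Who is affected.** Primary analyses require at least one of 15 risk factors (SAP 2.1). Age over 80 is read at the index date; the other 14 come from the baseline period (SAP 5.4).

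- *First record on the index date, aged 80 or under:* meets SAP 4.1.1, but all 14 other factors are 0. The patient is outside the primary cohort and falls in the lower-risk comparator of the unbalanced-cohort analyses in SAP 7.2.3.
- *First record on the index date, over 80:* enters the primary cohort through age. Diagnosis and drug terms in the propensity score (SAP 7.1.1) are 0. Age and sex are still used, and the scores keep their age and sex points: CHA2DS2-VASc is 2 for a man and 2 + 1 = 3 for a woman under SAP 5.4.
- *First record k days before the index date, k below 180, any age:* can qualify through a code from those k days, while OAC use in the other 180 - k days is unseen.

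**3. Start of the data.** Data begin on 1 March 2011, and 180 days later is 28 August 2011. A patient indexed before then cannot have a full lookback. Only warfarin can be indexed so early, since apixaban was approved in December 2012 (SAP 2).

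**4. Effect on the hazard ratio.** Let m_W and m_A be the shares of hidden prevalent users in the warfarin and apixaban arms, and u their hazard relative to true new users. Treating each arm's hazard as a simple mixture,

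factor on the HR = [1 - m_A(1 - u)] / [1 - m_W(1 - u)].

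None of these inputs is in the documents; all values below are assumptions.

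| m_W | m_A | u | Factor |
|---|---|---|---|
| 0.2 | 0.2 | 0.5 | 0.90/0.90 = 1.00 |
| 0.2 | 0.1 | 0.5 | 0.95/0.90 = 1.06 |
| 0.1 | 0.2 | 0.5 | 0.90/0.95 = 0.95 |
| 0.2 | 0.1 | 2 (= 1/0.5) | 1.10/1.20 = 0.92 |

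The factor can lie on either side of 1.

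**5. Room for a restricted analysis.** SAP 7.1.9 states 246 events per endpoint, and 7,846 and 10,789 patients. These reproduce:

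- Events = 4(1.960 + 0.842)² / (ln 0.7)² = 246.8.
- Major bleeding: mean rate (3.77% + 2.50%)/2 = 3.135%, and 246/0.03135 = 7,846.9.
- Stroke/SE: mean rate (2.77% + 1.79%)/2 = 2.28%, and 246/0.0228 = 10,789.5.

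The feasibility count is more than 10,000 per arm, so at least 20,000 in total. The stated sizes are still met after a loss of 1 - 7,846/20,000 = 61% for major bleeding and 1 - 10,789/20,000 = 46% for stroke/SE. Power at HR 0.7, with one person-year per patient as the SAP's figures imply and no allowance for variance from weighting:

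| Loss | Patients | Major bleeding | Stroke/SE |
|---|---|---|---|
| 0% | 20,000 | 0.99 | 0.97 |
| 20% | 16,000 | 0.98 | 0.93 |
| 40% | 12,000 | 0.93 | 0.84 |
| 50% | 10,000 | 0.88 | 0.77 |

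**The case against.** The best defence is that the risk-factor rule already acts as a partial history requirement. Everyone aged 80 or under in the primary cohort must have some record before the index date. A reader might infer that first-visit patients in general enter the primary analysis as OAC-naive and free of comorbidity. The documents do not support that: only those over 80 can, and even their scores are not all zero. But one record in the window is not 180 days of observation, so the third group in the working remains.

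A reader might also infer a one-directional bias in which hidden long-term warfarin users lower the warfarin rate and raise the HR by 1.03 to 1.18. That range follows from 1/(1 - m_W(1 - u)), with m_W = 0.1, u = 0.7 giving 1/0.97 and m_W = 0.3, u = 0.5 giving 1/0.85. It assumes no prevalent users in the apixaban arm and a lower hazard among prevalent users. The documents establish neither, and the same gap in the data applies to apixaban patients.

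Keeping the index date out is defensible for drugs. Heparin started with the OAC would otherwise count as baseline treatment, and the index OAC itself could count towards six oral drugs. This stands, and it rules out moving the whole baseline window to include day 0.

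Finally, Protocol 9.9 concedes claims misclassification and residual differences between groups, and SAP 7.1.8 plans E-values. Neither tests whether patients are new users. SAP 6 excludes patients lacking required data but does not define the term, and a covariate coded 0 is not missing.

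**Conclusion.** The gap is real and limited. OAC-naive status is not ensured by the criteria as written, and no planned analysis checks it. Within the primary cohort the exposed patients are those over 80 first seen on the index date and those of any age with a short recorded history. Truncation by the start of the data can affect only warfarin patients.

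Neither the number of such patients nor the size or direction of the bias can be derived from the documents. The factor of 1.06 is an illustration resting on an assumed 20% against 10% at relative hazard 0.5; equal shares and equal hazards give 1.00. The SAP's sample-size figures are not in question. This supports a cheap clarification and one sensitivity analysis. It does not show that the primary result would be wrong.

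**What to change.** 1. Report by arm the number of patients with no database record on or before day -180. Pre-specify a sensitivity analysis of both primary endpoints in patients who have such a record. This also implies an index date at least 180 days after the data begin.
2. State that diagnoses coded on the index date count as baseline for comorbidity covariates, diagnosis-based risk factors and diagnosis-based exclusions. Keep drug variables (heparins, antiplatelets, NSAIDs, polypharmacy) to the days before the index date.

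The cost is SAP wording, one count and one restricted rerun on data already held. The restricted set is smaller; on the SAP's assumptions its sizes hold up to the losses shown in the working, less whatever the weighting costs in precision. It favours patients established at the hospital over new referrals, so a different estimate could partly reflect a different population. One early record reduces unseen OAC use elsewhere but does not remove it. Item 2 also brings some first-visit patients aged 80 or under into the primary cohort, and their earlier OAC use is unobserved, so it should not be adopted without item 1.
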